Attachment 3b. Adult Study

The following provides information on the parameters and sample size calculation used in Table 2 for the adult study.

Sample size calculations were conducted with type 1 (" α error") set at .05 and type 2 error (" β error) set at .20. It was considered important that a study have a total sample size so that exposures could be categorized into tertiles (i.e., reference level, medium level, and high level) or preferably into quartiles (i.e., reference level, low, medium and high).

Studies were selected that were considered the most representative of U.S. populations exposed via drinking water to PFOA, PFOS and/or PFHxS as a result of the migration of these PFAS chemicals into ground water or surface water sources from the use of aqueous film forming foam (AFFF). The PFOS, PFOA and PFHxS results in the NHANES studies were used in many of the sample size calculations. For those outcomes not included in NHANES studies, the C8 studies were used. Where applicable studies from Taiwan or other major industrialized countries were also used.

Example:

Liver Function – Adults

In the C8 study (Darrow 2016), the mean alanine aminotransferase (ALT) level was 26 IU/L and the standard deviation was 19. The linear regression coefficient for the natural log ALT in the fifth quintile level of cumulative natural log PFOA was 0.058. Assuming that the reference group had an ALT level equal to the mean, the natural log of the mean ALT would be 3.26. Therefore the natural log of ALT for the fifth quintile cumulative log PFOA would be 3.32. Exponentiating 3.32 equals 27.6. The mean difference in the untransformed ALT is then 1.6.

Assuming a 95% CI and 80% power, the sample size = 2,214/group.

Thyroid Function – Adults (not included in Table 2)

In a study done by Shrestha 2015, the sample size was 87 adults aged 55-74. Mean and SD for TSH was 2.58 μ IU/mL and 1.47, respectively. The linear regression of the natural log TSH resulted in a coefficient for the natural log PFOS of 0.129. Using a PFOS level of 15 ng/mL, the natural log of 15 is 2.71; multiplied by 0.129 equals 0.35. The reference level TSH was assumed to be the median TSH of 2.15 μ IU/mL. The natural log of 2.15 is 0.77; adding 0.35 equals 1.12. Exponentiating 1.12 equals 3.06. The mean difference is then 3.06 – 2.15 = 0.91. The standard deviation of 1.47 was used for each group.

Assuming a 95% CI and 80% power, the sample size = 41/group.

Assuming a 95% CI and 95% power, the sample size = 68/group.

a. TSH

In Ji 2012, the sample size was 633, \geq 12 years of age and the median TSH level was 1.37 µIU/mL with an IQR of 0.90, 2.01. The standard deviation was estimated as the IQR range divided by 1.35: (2.01 - .90)/1.35 = 0.82. This standard deviation was assumed for each group. For TSH, the linear regression coefficients for PFOS and PFHxS were 0.062 and 0.013, respectively. Using a PFOS level of 15 ng/mL and a PFHxS level of 9 ng/mL, the mean difference for PFOS and PFHxS are 0.93 and 0.12, respectively.

Assuming a 95% CI and 80% power, the sample size = 13/group for PFOS

Assuming a 95% CI and 80% power, the sample size = 733/group for PFHxS

b. TT₄ (total thyroxine)

In Ji 2012, the sample size was 633, \geq 12 years of age and the median TT₄ level was 7.4 µg/dL and the IQR was 6.7, 8.1. The standard deviation was estimated: (8.1 – 6.7)/1.35 = 1.04. This standard deviation was assumed for each group. For TT₄, the linear regression coefficients for PFOS and PFHxS were -0.021 and - 0.007, respectively. Using a PFOS level of 15 ng/mL and a PFHxS level of 9 ng/mL, the mean difference for PFOS and PFHxS are -0.32 and -0.06, respectively.

Assuming a 95% CI and 80% power, the sample size = 166/group for PFOS

Assuming a 95% CI and 80% power, the sample size = 4,716/group for PFHxS

Sample sizes for the categorical outcomes in Table 2 were based on the following prevalences in adults:

Hypercholesterolemia: 15% Hyperuricemia: 24% Thyroid disease: 6.5% (reported and confirmed by medical records); 11.5% (reported only) Elevated ALT: 11.2% Elevated GGT: 14% Elevated bilirubin: 1.1% Osteoporosis: 5% Osteoarthritis: 7.6% Cardiovascular disease: 13% Ulcerative colitis: 0.5% Rheumatoid arthritis: 1.2%

Health related Endpoints Not shown in Table 2:

Chronic kidney disease: 1.4% Liver disease: 2% Hypertension: 37% Pregnancy-induced hypertension: 8.5% Endometriosis: 7% Lupus: 0.2% Multiple sclerosis: 0.32% Kidney cancer: 0.3%

Multi-site Study – Eligibility Screening Script

Multi-site Study Eligibility Screening Script Flesch-Kincaid Readability Score – 5.8

> Form Approved OMB No. 0923-XXXX Exp. Date xx/xx/201x

ATSDR estimates the average public reporting burden for this collection of information as 10 minutes per response, including the time for reviewing instructions, searching existing data/information sources, gathering and maintaining the data/information needed, and completing and reviewing the collection of information. An agency may not conduct or sponsor, and a person is not required to respond to a collection of information unless it displays a currently valid OMB Control Number. Send comments regarding this burden estimate or any other aspect of this collection of information, including suggestions for reducing this burden to CDC/ATSDR Information Collection Review Office, [name]; ATTN: PRA (0923-xxxx).

(This script will be used to screen adult and parent/child volunteers who respond to the NH DHHS Invitation Letter to former Biomonitoring Program participants. They will be instructed to call ATSDR on the toll-free number.) [SHADED TEXT DENOTES INFORMATION COLLECTION]

Hello. My name is ______. I'd like to thank you for calling about the **Multi-site PFAS Health Study**.

I understand that you received a letter from the [insert institution name] about volunteering for the Multi-site Study. As you know, the Agency for Toxic Substances and Disease Registry, or ATSDR for short, is funding the study and [insert study investigators institution name] would like to recruit people for the Multi-site Study who reside at [insert site]. If there are more people in your house who took part and are interested, I'd like to start with you first.

[Screening Questions for ADULT – If a PARENT calls who is not going to enroll as an ADULT > go directly to Screening Questions for PARENT/CHILD]

A1. I'm happy to hear that you received the invitation letter as a resident of [insert site]. Are you 18 years or older?

- **YES** > go to A2.
- NO (under 18) > OK, can I speak to your parent or guardian? [becomes PARENT ONE] > go to Screening Questions for PARENT/CHILD.

A2. Have you ever worked as a firefighter or ever participated in training exercises using firefighting, or AFFF, foam?

- **YES** > I'm sorry. People who ever worked as a firefighter or used firefighting foam are not eligible for this study. > go to Screening Questions for PARENT/CHILD.
- **NO** > go to A3.

A3. Have you ever worked at industrial facilities that used PFAS chemicals in the manufacturing process?

- **YES** > I'm sorry. People who ever worked at facilities using PFAS chemicals are not eligible for this study. > go to Screening Questions for PARENT/CHILD.
- NO > Thank you very much. You are eligible to take part in the Multi-site Study as an adult participant. > go to A4.

A4. Are you in prison or under house arrest?

- **YES** > I'm sorry. The federal regulations say that people who are in prison or under house arrest cannot be in this study. > go to Screening Questions for PARENT/CHILD.
- NO > Thank you very much. You are eligible to take part in the Multi-site as an adult participant. > go to A4.

A5. If you want to enroll in the Multi-site Study as an adult participant, I will need your contact information to send you some recruitment materials and to set up an appointment.

Record ADULT Contact Information

•	FIRST NAME						
•	LAST NAME						
•	STREET ADDRESS						
•	CITY						
•	STATE						
•	ZIP CODE						
•	DATE OF BIRTH		/ _	_ / _	> verify	v age el	igibility
•	WORK PHONE NU	MBER					
•	HOME PHONE NU	MBER					
•	CELL PHONE NUM	IBER					
•	EMAIL						

After the call is over, enter the assigned ADULT STUDY ID number to begin tracking enrollment and biospecimen sample logistics. Be sure to link the ID numbers for an individual who has both an ADULT STUDY ID and one or more PARENT STUDY IDs.

•	ADULT STUDY ID	

A6. The study interview will take place at our central study office at (address). We would like to conduct the study there, but we know some people may find it difficult to travel. For some cases, we are willing to send an interview team to their homes as long as it is within a one-hour drive from the central office. Which location works best for you?

Record Appointment Location

CLINIC OFFICEADULT HOME

A7. Let's pick a good day and time for you. > Record Appointment Information

A8. Thank you for your interest. We will mail you a packet of information including consent forms that shows what to expect at your appointment. We will also mail instructions. They will tell you how to prepare and what to bring.

A8. Adult participants may also enroll as parents of children in this research. Are there any children in your household who received an invitation letter?

- **YES** > go to Screening Questions for PARENT/CHILD.
- **NO** > OK. Thank you very much for your interest. We will mail your Appointment Packet shortly. If there are any other adults in your household who received an invitation letter, I will be happy to speak to them now, or at another more convenient time. Thanks again. > *When additional adults are available, begin at A1*.

[Screening Questions for PARENT/CHILD]

For this research study, ATSD and [insert study investigators institution name] are recruiting children who reside at [insert site] and received an invitation letter from the [insert state; whom?] Health Department. We are looking for about [insert as applicable] interested parent/child pairs to enroll. A parent may also enroll with more than one child.

P1. For each child, 4-17 years old, who received a letter and is interested in taking part in the Multi-site Study, I need to speak to the parent or guardian who wants to enroll with his or her child. We think it is best if the child's birth mother enrolls. That is because we will ask a lot of questions about when your child was a baby. Am I speaking to the right person?

- **YES** > Thank you. I need to find out a bit more about each child who wants to be in the Multi-site Study. If you have more than one, let's start with the youngest.
- NO > OK, I'd like to speak to that parent or guardian. If this isn't a good time, he or she can call our office later. If now is a good time, let's start with the youngest.
 - *If correct parent not available, stop* > OK, we will be waiting for that parent to call our office. Thanks very much for your interest.
 - If correct parent available, go to P2.

P2. How old is [CHILD 1; CHILD 2; CHILD 3; etc.]?

- AGE ____ years > eligible age is 4-17 years >
 - If not age eligible, go to P2a.
 - If age eligible, go to P3.

P2a. I'm sorry. We are looking for children 4-17 years. Do you have other children who are 4-17 years?

- **YES** > OK, let me find out more about them. > *go back to P2*.
- NO > Thank you very much for calling us today. It appears that your children are not eligible to take part in the Multi-site Study. We appreciate your interest in this research.

[ADD IF EXPOSURE OCCURRED WITHIN 15 YEARS OF START OF THE STUDY]

P3. Has [CHILD 1; CHILD 2; CHILD 3; etc.]'s birth mother ever worked as a firefighter or ever participated in training exercises using firefighting, or AFFF, foam?

• **YES** > I'm sorry. Children whose birth mother ever worked as a firefighter or used firefighting foam are not eligible for this study. If you have other children who are 4-17 years, let me ask these same questions about him or her. > go back to P2. If no more children, go to P3a.

P3a. Thank you very much for calling us today. It appears that your children are not eligible to take part in the Multi-site Study. We appreciate your interest in this research.

• **NO** > go to P4.

P4. Has [CHILD 1; CHILD 2; CHILD 3; etc.]'s birth mother ever worked at industrial facilities that used PFAS chemicals in the manufacturing process?

• YES > I'm sorry. Children whose birth mother ever worked at facilities using PFAS chemicals are not eligible for this study. If you have other children who are 4-17 years, let me ask these same questions about him or her. > go back to P2. If no more children, go to P4a.

P4a. Thank you very much for calling us today. It appears that your children are not eligible to take part in the Multi-site Study. We appreciate your interest in this research.

• NO > OK. You and your child are eligible to enroll in the Multi-site Study as a child/parent pair. > go to P5.

P5. Is your child in prison or under house arrest?

- **YES** > I'm sorry. The federal regulations say that people who are in prison or under house arrest cannot be in this study. > go to Screening Questions for PARENT/CHILD.
- NO > Thank you very much. Your child is eligible to take part in the Multi-site Study as a participant. > go to P6.

P6. I will need your contact information to send you some recruitment materials and to set up an appointment.

P5a. Record PARENT 1 Contact Information

•	FIRST NAME	
•	LAST NAME	
•	STREET ADDRESS	
•	CITY	
•	STATE	
•	ZIP CODE	
•	WORK PHONE NUMBER	
•	HOME PHONE NUMBER	
•	CELL PHONE NUMBER	
•	EMAIL	

P6b. Record CHILD 1 Contact Information

•	FIRST NAME
•	LAST NAME
•	STREET ADDRESS
•	СІТҮ
•	STATE
•	ZIP CODE
•	DATE OF BIRTH / // > verify age eligibility
•	PARENT 1 STUDY ID

CHILD 1 STUDY ID

P6c. The study interview will take place at our central study office at (address). We would like to conduct the study there, but we know some people may find it difficult to travel. For some cases, we are willing to send an interview team to their homes as long as it is within a one-hour drive from the central office. Which location works best for you?

Record Appointment Location

```
    CLINIC OFFICE
```

ADULT HOME

P6d. Let's pick a good day and time for you. > Record Appointment Information

P7. If you have another eligible child who would like to enroll, I will fill in his or her contact information, too. Let me go back through the screening questions. > go back to P2. If no more children, go to P6a.

P7a. Thank you very much for your interest. We will mail your child's Appointment Packet shortly. Thanks again.

P7b. Record PARENT 2 Contact Information

•	FIRST NAME	(enter "SAME AS PARENT 1" if applicable > go to P6c)
•	LAST NAME	
•	STREET ADDRESS	
•	CITY	
•	STATE	
•	ZIP CODE	
•	WORK PHONE NUMBER	
•	HOME PHONE NUMBER	
•	CELL PHONE NUMBER	
•	EMAIL	

P7c. Record CHILD 2 Contact Information

•	FIRST NAME			
•	LAST NAME			
•	STREET ADDRESS		(enter	"SAME AS PARENT 1" if applicable > go to P6d)
•	CITY			
•	STATE			
•	ZIP CODE			
•	DATE OF BIRTH	/ > verify age elig	ibility	

•	PARENT 2 STUDY ID	
•	CHILD 2 STUDY ID	

P7d. Which location for your interview works best for you?

Record Appointment Location

CLINIC OFFICE

ADULT HOME

P7e. Let's pick a good day and time for you. > Record Appointment Information

P8. If you have another eligible child who would like to enroll, I will fill in his or her contact information, too. Let me go back through the screening questions. > go back to P2. If no more children, go to P7a.

P8a. Thank you very much for your interest. We will mail your children's Appointment Packets shortly. Thanks again.

P8b. Record PARENT 3 Contact Information

•	FIRST NAME	[]	(enter "SAME AS PARENT 1" if applicable > go to P7c)
•	LAST NAME		
•	STREET ADDRESS		
•	CITY		
•	STATE		
•	ZIP CODE		
•	WORK PHONE NUMBER		
•	HOME PHONE NUMBER		
•	CELL PHONE NUMBER		
•	EMAIL		

P8c. Record CHILD 3 Contact Information

•	FIRST NAME	
•	LAST NAME	
•	STREET ADDRESS	(enter "SAME AS PARENT 1" if applicable > go to P7d)
•	CITY	
•	STATE	
•	ZIP CODE	
•	DATE OF BIRTH	/ > verify age eligibility
•	PARENT 3 STUDY ID	

P8d. Which location for your interview works best for you?

Record Appointment Location

CHILD 3 STUDY ID

CLINIC OFFICEADULT HOME

P8e. Let's pick a good day and time for you. > Record Appointment Information

•	DAY	
•	DATE	/
•	TIME	: AM PM

P9. (CLOSING REMARKS) Thank you very much for your interest. We will mail your [child's/children's] Appointment Packet(s) shortly. Thanks again.

P10. Data Linkages

After the call is over, enter the assigned PARENT (1,2,3, etc.) STUDY ID number(s) to begin tracking enrollment and biospecimen sample logistics for each child. Be sure to link the ID numbers for an individual who has both an ADULT STUDY ID and one or more PARENT STUDY ID aliases.

ADULT STUDY ID
 (IF APPLICABLE ALIAS)

•	PARENT 1 STUDY ID	
•	PARENT 2 STUDY ID	(IF APPLICABLE ALIAS)
•	PARENT 3 STUDY ID	(IF APPLICABLE ALIAS)

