6 For adults, **Table 2** (and **Attachment 3b**) provide the sample size calculations for several health outcomes 7 of interest assuming a type 1 (" α error") of .05 and type 2 error (" β error) of .20. In this exposure based 8 study we assume an appropriate coverage of range of exposures that will enable 9 stratification/categorization to tertiles or quartiles of exposure. Per stratum estimates of needed sample 10 size (e.g. first vs. fourth quartile) have been calculated based on different measures of association such as 11 odds ratios or detected mean difference.

12 The proposed sample size of 6,000 adults (equally of both sexes) is large enough to effectively evaluate 13 many of the health outcomes identified in the Pease Feasibility Assessment literature review. For example, for outcomes like elevated lipids levels (cholesterol) or uric acid, the range of 229 to 660 14 15 participants per stratum (i.e. quartile) or 200 to 550 per stratum, respectively, given observed differences would be needed. That would translate to overall sample size of about 800 to 2,600 participants being 16 sufficient to detect differences at the specified level of precision and power (Steenland, 2009, 2010; Fisher 17 18 2013; Shankar 2011). Similar sample sizes would also be required to compare other common health 19 outcomes such as cardiovascular disease (Shankar 2012). Larger samples sizes would be needed for liver 20 function or osteoarthritis, with a total sample in the range of 3,000 to 4,000 subjects (Uhl 2013; Gallo 21 2012; Steenland 2010).

22 For thyroid disease and thyroid function, a total sample size of 6,000 may be sufficient although probably 23 not optimal. However, NHANES studies of thyroid function and thyroid disease obtained statistically 24 significant findings with total sample sizes considerably less than 6,000 (Melzer 2010; Wen 2013). 25 NHANES studies of liver function also obtained statistically significant findings with total sample sizes 26 considerably less than 6,000 (Gleason 2015; n=4333). For biomarkers of immune function (e.g., immunoglobulins, C-reactive protein and cytokines) and fatty liver disease, there was insufficient 27 28 information to calculate sample sizes. However, a total sample size of 6,000 should be sufficient to 29 evaluate these biomarkers as we assumed similar endpoint differences of those outcomes.

For ulcerative colitis, a sample size of 6,000 might be sufficient if the effect size in the C8 study (i.e.,

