 OR=3.05) was consistent for PFOA serum levels considerably lower than those in the C8 study. For more

- 1 modest effect sizes (e.g., ORs < 2.75), a total sample size of 6,000 would not be adequate to evaluate
- 2 associations with ulcerative colitis.
- 3 In addition, several epidemiological studies of adults exposed to PFAS that reported robust statistical
- 4 associations with these health outcomes had smaller sample sizes than the one proposed for the Multi-
- 5 site Study, e.g., NHANES studies (Nelson 2010, Wen 2013), a C8 longitudinal study (Fitz-Simon 2013), a C8
- 6 immune study (Looker 2014), and studies in China (Fu 2014) and Korea (Ji 2012).
- 7 In summary, a total sample size of ≥6,000 in multi-site study should be sufficient to evaluate a broad range
- 8 of biomarkers and outcomes such as lipids (and hypercholesterolemia), uric acid (and hyperuricemia),
- 9 cardiovascular disease, osteoarthritis, immune biomarkers and biomarkers for fatty liver disease. It also
- 10 may be sufficient to evaluate thyroid disease, thyroid function and liver function.
- 11 **Table 2.** Sample size estimations for selected health-related endpoints in Adult Study.

Health-related Endpoint	Relevant Study	Observed Effect Size	Assumptions	Sample Size/Stratum α error = .05 β error = .20
Total Cholesterol (mg/dL)	Steenland 2009, C8 46,294 aged ≥18 yrs	PFOS, mean serum level = 19.6 μg/L, 10 th vs 1 st decile:+11 mg/dL	SD=41.9	228/stratum
High cholesterol		4 th vs 1 st quartile, OR=1.51	Prevalence=15%	660/stratum
High Cholesterol	Fisher 2013, Canada	PFHxS, mean serum level = 2.2 μ g/L, 4 th vs 1 st quartile, OR=1.57	Prevalence=44%	290/stratum
Cardiovascular disease	Shankar 2012, NHANES 1,216 aged ≥40 years	PFOA mean serum level = 4.2 μ g/L, 4 th vs 1 st quartile: OR=2.01	Prevalence = 13%	250/stratum
Uric Acid	Steenland 2010, C8 53,458 aged ≥20 yrs	PFOS mean serum level = 20.2 μg/L, 10 th vs 1 st decile: +0.22 mg/dL	SD=1.55	780/stratum
		Hyperuricemia, 5 th vs 1 st quintile: OR=1.26	Prevalence:24%	1,525/stratum
Uric Acid	Shankar 2011, NHANES 3,883 aged ≥20 yrs	PFOA mean serum level = 3.5 μg/L, 4 th vs 1 st quartile: +0.44 mg/dL	SD = 2.5	507/stratum
		Hyperuricemia, 4 th vs 1 st quartile: OR=1.97	Prevalence: 19.2%	200/stratum
		PFOS mean serum level = 17.9 μg/L		550/stratum

		Hyperuricemia, 4 th vs 1 st quartile: OR=1.5		

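### Section 3.3.2 calls 6,000 adults possibly sufficient for thyroid function, but Attachment 3b needs 4,716 per group for TT4 with PFHxS, and its adult thyroid sizes subtract no reference exposure level

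*Protocol*

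**What the plan says.** Section 3.3.2 (Adults) describes the design comparison as one between exposure strata, for example first against fourth quartile, and gives sizes per stratum at 5% type 1 and 20% type 2 error. On thyroid outcomes it says: "For thyroid disease and thyroid function, a total sample size of 6,000 may be sufficient although probably" and the sentence ends by calling that number not optimal. The summary paragraph of the same section says the sample "may be sufficient to evaluate thyroid disease, thyroid function and liver function", without that qualification.

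The adult thyroid-function sizes are not in Table 2. They appear only in Attachment 3b, which gives five at 80% power:

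- TSH with PFOS, from a study of 87 adults aged 55–74: 41 per group.
- TSH with PFOS, from a Korean study of 633 people: "the sample size = 13/group for PFOS".
- TSH with PFHxS, Korean study: 733 per group.
- TT4 with PFOS, Korean study: 166 per group.
- TT4 with PFHxS, Korean study: "the sample size = 4,716/group for PFHxS".

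The way the mean differences were built is also stated. For the study of 87 adults: "Using a PFOS level of 15 ng/mL, the natural log of 15 is 2.71; multiplied by 0.129 equals 0.35". For the Korean study, each coefficient is multiplied by 15 ng/mL for PFOS or 9 ng/mL for PFHxS.

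**The concern.** There are two linked problems.

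First, the adequacy statement in the body makes no exception for TT4 with PFHxS, although the attachment's own requirement for that pairing is about three times the size of a quartile. The pairing is not marginal. TT4 is named in the adult thyroid hypothesis (section 2.5.2), PFHxS is one of the three named exposures, and the protocol gives the lack of PFHxS evidence as a reason for the study. Someone reading only section 3.3.2 and Table 2 never sees 4,716.

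Second, a coefficient times an exposure level is the difference between that level and zero (or 1 ng/mL when the exposure is logged). That is not a contrast between two strata of an exposed community. With the upper level held fixed, any reference above zero (or 1) shrinks the difference and raises the required size.

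At stake is how a null categorical result for PFHxS and TT4 would be read, and whether the attachment's figures can serve as planning figures.

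**Working it through.** **Inputs.** From Attachment 3: the two-sided formula for a mean difference. From Attachment 3b: TT4 SD 1.04, coefficients −0.021 (PFOS) and −0.007 (PFHxS), stated differences −0.32 and −0.06. For TSH in the Korean study: SD 0.82, coefficients 0.062 and 0.013, stated differences 0.93 and 0.12. For TSH in the study of 87 adults: SD 1.47, log-log coefficient 0.129, reference TSH 2.15, stated difference 0.91. From Attachment 2: NHANES adult 50th to 95th percentiles of 5.60 to 19.5 µg/L (PFOS) and 1.40 to 5.50 µg/L (PFHxS). From section 3.3.2: 6,000 adults, so 1,500 per quartile or 2,000 per tertile.

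**Step 1: reproduce the plan's figures.** With equal groups and equal SDs, n = 2σ²(1.96 + 0.84)²/Δ².

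- TT4–PFHxS: 2 × 1.04² × 7.849 / 0.06² = 4,716. Matches.
- The same formula returns 166 (TT4–PFOS), 13 and 733 (TSH, Korean study) and 41 (TSH, 87 adults). All match.
- With the unrounded difference 9 × 0.007 = 0.063, TT4–PFHxS needs 4,278.

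**Step 2: compare with the planned strata.** 4,716 per group means 9,432 adults for two groups, 14,148 for tertiles and 18,864 for quartiles. Power = Φ(Δ/(σ√(2/n)) − 1.96):

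| Split of 6,000 | n per group | Power, Δ = 0.06 | Power, Δ = 0.063 |
|---|---|---|---|
| Quartiles | 1,500 | 35% | 38% |
| Tertiles | 2,000 | 45% | 48% |
| Halves | 3,000 | 61% | 65% |

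For quartiles: 0.06/(1.04 × √(2/1500)) = 1.58, and Φ(1.58 − 1.96) = 0.35. The smallest TT4 difference detectable with 80% power at 1,500 per group is 2.80 × 1.04 × √(2/1500) ≈ 0.106.

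**Step 3: the implied exposure contrasts.** 0.129 × ln 15 compares 15 with 1 ng/mL, because ln 1 = 0. 0.062 × 15 and 0.021 × 15 compare PFOS 15 with 0. 0.013 × 9 and 0.007 × 9 compare PFHxS 9 with 0. So the PFHxS sizes, including 4,716 itself, rest on 9 against 0.

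**Step 4: put in a reference level.** The study's own strata are unknown. As an assumption, take the NHANES adult medians (5.60 and 1.40) as the reference and keep 15 and 9 as the upper levels.

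| Pairing | Difference | Stated n | n with reference |
|---|---|---|---|
| TSH–PFOS, 87 adults | 2.15 × [(15/5.6)^0.129 − 1] = 0.291 | 41 | about 400 |
| TSH–PFOS, Korean | 0.062 × 9.4 = 0.583 | 13 | about 32 |
| TT4–PFOS, Korean | 0.021 × 9.4 = 0.197 | 166 | about 436 |
| TSH–PFHxS, Korean | 0.013 × 7.6 = 0.099 | 733 | about 1,080 |
| TT4–PFHxS, Korean | 0.007 × 7.6 = 0.053 | 4,716 | about 6,000 |

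For TT4–PFHxS at 1,500 per quartile, 0.0532/(1.04 × √(2/1500)) = 1.40 and Φ(1.40 − 1.96) ≈ 0.29. If the upper PFHxS level is also lowered to the listed 95th percentile (5.5 against 1.4), TSH–PFHxS needs about 3,700 per group and TT4–PFHxS about 20,600.

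**The case against.** The strongest reply is that the thyroid statement is hedged and broad. It says probably not optimal, it covers thyroid function generally, and four of the five stated sizes (13, 41, 166, 733) fit within a quartile. Section 3.3.2 also points to NHANES thyroid studies that reached significance with far fewer than 6,000 people, and warns that all the sizes need cautious reading. This stands to the extent that 4,716 does not overturn the general statement. A reader might infer that 6,000 adults are too few for thyroid function as a whole; the documents do not support that. They do support saying that one named pairing is outside the statement, which the text never says. About 35% power is well short of merely sub-optimal.

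Second, section 3.10 also plans regression on continuous PFAS and spline models, so 35% is not the power of every analysis. This stands. Power for a slope of 0.007 depends on the spread of PFHxS, which is not given; 80% power with 6,000 adults would need an exposure SD of about 5.4 ng/mL, from 2.80 × 1.04/(0.007 × √6000).

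Third, the cohort's quartiles are unknown and NHANES medians describe background exposure. This is why step 4 is labelled an assumption. The direction does not depend on it while the upper level is held: a positive PFHxS reference, or a PFOS reference above 1 ng/mL, raises the size.

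Fourth, section 3.10 bases interpretation on effect magnitude and confidence intervals, not significance alone. That softens the harm from a null result but does not reconcile the text with the attachment.

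A reader might also extend the point to the immune and fatty-liver markers, for which section 3.3.2 says 6,000 should suffice without a calculation. That does not hold. The protocol discloses that it lacked the information, and the difference detectable with 80% power at 1,500 per group is 2.80 × √(2/1500) ≈ 0.10 SD. That is small and consistent with the claim.

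**Conclusion.** The point holds in limited form. The arithmetic in Attachment 3b reproduces. The defects are a mismatch between attachment and text, and a missing reference level.

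- For the categorical TT4–PFHxS contrast, 6,000 adults are not adequate by the protocol's own effect size: power is about 35% in quartiles and 45% in tertiles, or 38% and 48% with the unrounded difference.
- The adult thyroid sizes in Attachment 3b are too small for the stratum comparison that section 3.3.2 describes. With NHANES medians as the assumed reference, the consequence is confined to PFHxS. TT4 rises to about 6,000 per group (quartile power about 29%). TSH rises to about 1,080, which still fits a quartile but fails if the top level is nearer 5.5 than 9 ng/mL.
- The PFOS pairings remain feasible, at most about 436 per group.

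These figures rest on the external coefficients and SDs that the protocol adopted, equal groups, a two-sided 5% level and no covariate adjustment.

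**What to change.** 1. In section 3.3.2 and its summary paragraph, add that the quartile or tertile contrast of TT4 by PFHxS is not adequately powered at 6,000 adults (about 35–45% for the effect used in Attachment 3b), and that this figure does not describe the continuous-exposure regression. Carry the not-optimal qualification into the summary.
2. In Attachment 3b, recompute the adult TSH and TT4 sizes from the difference between a stated top-stratum and a stated reference-stratum serum level, for both PFOS and PFHxS, and give the source of each level. Where the reference is uncertain, show a small range.
3. Refer from section 3.3.2 to these sizes, since Table 2 omits them.

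The cost is revised text and less favourable stated figures. No additional participants and no change in design are needed.
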